4.3 Withdrawal Criteria

Participation of a patient in this clinical study may be discontinued for any of the following reasons:

- The patient withdraws consent or requests discontinuation from the study for any reason;
- Occurrence of any medical condition or circumstance that exposes the patient to substantial risk and/or does not allow the patient to adhere to the requirements of the protocol;
- Any SAE, clinically significant adverse event, severe laboratory abnormality, intercurrent illness, or other medical condition which indicates to the Investigator that continued participation is not in the best interest of the patient;
- Pregnancy;
- Requirement of prohibited concomitant medication;
- Patient failure to comply with protocol requirements or study-related procedures; or
- Termination of the study by the Sponsor or the regulatory authority.

For patients in whom the creatinine clearance drops below 70 mL/min after baseline, the Investigator should repeat serum creatinine at the local laboratory once they receive the abnormal laboratory result to confirm the value. The Investigator may withdraw the patient from the study when a dose adjustment for imipenem is necessary or when patient safety is at risk. However, if the Investigator believes that the creatinine clearance decrease is not clinically significant or will quickly reverse, the Medical Monitor will be contacted to discuss if the patient may continue in the study or should be withdrawn.

If a patient withdraws prematurely from the study due to the above criteria or any other reason, study staff should make every effort to complete the full panel of assessments scheduled for the EOT Visit, and the patient should be followed through the LFU Visit. If a patient withdraws after the EOT Visit, study staff should make every effort to complete the full panel of assessments scheduled for the study visit following the date of withdrawal (TOC Visit or LFU Visit), as applicable. The reason for subject withdrawal must be documented in the electronic case report form (eCRF).

In the case of patients lost to follow-up, attempts to contact the subject must be made and documented in the patient's medical records.

Withdrawn subjects will not be replaced.

5 STUDY TREATMENTS

5.1 Treatment Groups

Study drug will be administered IV in a double-blind design. The study will be constructed with 2 treatment arms (2:1) as follows:

- 1 g ETX2514/1g sulbactam IV administered q6h over 3 hours, or
- Matching placebo IV administered q6h over 3 hours.

In addition, all patients will be administered background therapy with 500 mg IV imipenem/cilastatin q6h infused over 30 minutes. Infusions of study drug will occur q6h for 7 calendar days, with a prolongation of therapy up to 14 days if clinically indicated in patients with concurrent bacteremia.

5.2 Rationale for Dosing

The doses of ETX2514 and sulbactam to be evaluated in this study have been selected based on PK data generated in nonclinical experiments and a Phase 1 PK study that evaluated SAD and MAD of ETX2514, evaluation of safety in Good Laboratory Practice toxicology studies, and PK/PD. Data from these studies are provided in more detail in the Investigator's Brochure.

ETX2514 1 g was generally well tolerated in multiple doses in the Phase 1 study. Sulbactam 1 g was generally well tolerated as a single dose in the Phase 1 study. The total daily dose of sulbactam being used in the current study is consistent with the US Product Circular for Unasyn, in which the maximum approved daily dose for sulbactam is 4 g, which is equivalent to 1 g sulbactam q6h.

The ETX2514SUL regimen of 1 g ETX2514/1 g sulbactam infused over 3 hours q6h is consistent with the PK/PD targets established for a susceptibility breakpoint against *A. baumannii* of 4 mg/L.

5.3 Randomization and Blinding

Qualifying patients will be randomized in a 2:1 ratio to receive 1 g ETX2514/1 g sulbactam or placebo via the Interactive Response Technology (IRT) system. All patients will receive 500 mg IV imipenem/cilastatin q6h.

Randomization will be stratified by baseline diagnosis (symptomatic cUTI versus AP). A manual will be provided that describes the IRT system and includes user instructions.

At least 30% of patients will have a diagnosis of AP at study entry.

Patients who have received a single dose of short-acting antibiotic (see Appendix C for a list of allowed and disallowed antibiotics) for cUTI or AP within 24 hours of randomization will comprise a maximum of approximately 25% of the study enrollment. Patients who have received any potentially therapeutic and long-acting antibiotic for more than 24 hours within the 72-hour window of the start of administration of the first dose of study drug will be excluded from the study.

A randomization notification will be sent to the unblinded pharmacist (or appropriately qualified unblinded designee) at the site. A blinded randomization notification will be sent to the appropriate blinded site personnel.

The Investigator, site personnel, Sponsor, and the Sponsor’s designees involved in monitoring, data management, and other aspects of the study will be blinded to treatment assignment. An unblinded site monitor will be assigned to review unblinded pharmacy data and will follow documented procedures to ensure that the blind is maintained throughout the study.

5.4 Breaking the Blind

The Sponsor designee (eg, IRT vendor, etc.) will have a designated randomization administrator who will maintain the randomization codes in accordance with Standard Operating Procedures to ensure that the blind is properly maintained and that only Sponsor personnel who require knowledge of treatment assignments will be unblinded (eg, staff involved in maintaining the randomization codes or SAE reporting).

Unblinding should only occur in the event of an emergency or adverse event for which it is necessary to know the study drug treatment to determine an appropriate course of therapy. If the patient’s study drug must be unblinded, the Investigator or qualified designee should contact IRT, but not the site’s unblinded pharmacist, for the study drug information. The IRT documentation indicating the blind break must be retained with the patient’s source documentation in a way as to not unblind the treatment assignment to other site or Sponsor personnel.

If possible, the Investigator should attempt to contact the site monitor or the Medical Monitor prior to unblinding in order to get additional information about the study drug. If not possible, the Investigator should notify the site monitor or Medical Monitor as soon as possible of the unblinding without disclosing the treatment assignment of the unblinded patient. The Investigator must document the patient’s identification, reason for breaking the blind, and the date and time for breaking the blind.

After the database is locked and the Statistical Analysis Plan (SAP) is final, the study blind codes will be broken.

5.5 Prior and Concomitant Medications and/or Procedures

5.5.1 Excluded Medications and/or Procedures

Treatment with any of the following concomitant medications or procedures is prohibited:

[REDACTED]

- Methotrexate;
- Ganciclovir;
- Valproic acid or divalproex sodium;
- Any cancer chemotherapy, immunosuppressive medications for transplantation, or medication for rejection of transplantation;
- Any additional or adjunctive non-study-specific antibiotic therapy administered with the intention of treating cUTI, AP, or other infection. Agents with Gram-positive only coverage (eg, vancomycin, daptomycin, or linezolid) for suspected or identified Gram-positive organisms may be considered, as deemed necessary by the Investigator;

- Any antifungal therapy other than topical antifungal or a single oral dose of any antifungal treatment for vaginal candidiasis; or
- Bladder irrigations with any antiseptic or antibiotic.

5.5.2 Restricted Medications and/or Procedures

Treatment with any of the following concomitant medications or procedures is restricted:

- Antibiotics for the treatment of *Clostridium difficile* (eg, fidaxomicin), or
- Topical antibiotics other than those used for bladder irrigation.

5.5.3 Documentation of Prior and Concomitant Medication Use

Reasonable effort will be made to determine all relevant treatments (including all antibiotics, prescription and non-prescription medications, herbal medications and vitamin supplements, supportive therapies, and non-pharmacologic treatments) received within 14 days before the first dose of study drug and during the study. The name, route of administration, dose, frequency, indication, and duration of the treatment will be recorded in the eCRF. The date and time of start and stop of any antibiotic therapy received within 14 days before the first dose of study drug and during the study will also be recorded.

Patients cannot participate in any other investigational medication trial while participating in this study, or have taken any investigational product within 30 days prior to the first dose of study drug in this study.

5.6 Drug Supplies

5.6.1 Formulation and Packaging

██
██
██
██

Study drugs will be labeled according to the requirements of local law and legislation, as well as current Good Manufacturing Practice and Good Clinical Practice (GCP) guidelines.

5.6.2 Study Drug Preparation and Dispensing

An unblinded pharmacist (or qualified designee) will prepare the study drug according to the requirements outlined in the Pharmacy Manual. The IV bags will be labeled with the date and time of study drug preparation and patient identification number using the study supplied labels and will be transferred to the blinded study staff for administration to the patient. Reconstituted study drug should be administered according to the requirements outlined in the Pharmacy Manual.

5.6.3 Study Drug Administration

The unblinded pharmacist (or qualified designee) will be responsible for providing blinded study personnel with study drug ready for IV infusion. Patients will receive treatment in accordance with the blinded randomization schedule administered via an IRT system. Patients will receive randomized treatment administered as described in the Pharmacy Manual.

Patients will receive all infusions by drip infusion or programmable infusion pump while seated or partially reclined in bed. The times at which each infusion is started and stopped must be recorded. If a dose is interrupted for more than 10 minutes, the interruption and reason for interruption should be noted in the source documents. Any missed dose should also be noted in the source documents with the reason for the missed dose. Study drug infusions will be administered q6h (± 15 minutes). Infusions that fall outside of the q6h (± 15 minutes) dosing schedule will be considered protocol deviations. It is critical that administration and infusion time be captured in the eCRF based on actual time. Windows for administration and infusion provided should be used sparingly, and the patient should remain on schedule based on the q6h administration requirement.

Dosing time is relative to the start of infusion. For additional information on study drug product dilution, infusion volumes, and dispensing instructions, refer to the Pharmacy Manual.

5.6.4 Treatment Compliance

The infusion date and start and stop times will be recorded in the source documents and eCRF. Treatment compliance will be calculated based on the number of doses received and expected as detailed in the SAP.

5.6.5 Storage and Accountability

The unblinded pharmacist or designated unblinded study personnel will ensure that all study drugs are stored in a locked, secure area with limited access. Study drugs will be stored under recommended storage conditions per the label and in accordance with the Pharmacy Manual.

The date and time of preparation of study drug will be recorded on the IV bags. Refer to the Pharmacy Manual for additional information.

The Investigator is responsible for maintaining a current record of inventory/drug accountability. Vials may not be discarded until inventory and drug accountability is performed by the unblinded monitor.

6 STUDY PROCEDURES

A detailed schedule of procedures is provided in Appendix A.

6.1 Informed Consent

Informed consent must be obtained before any study procedures are performed. The ICF will be signed at Screening. As permitted by local law and institutional Standard Operating Procedures, in cases of a lack of decision-making capacity, informed consent on behalf of the patient may be provided by a legally authorized representative.

6.2 Screening (-48 hours to Day 1)

Screening can occur up to 48 hours before the first dose of study drug. All Screening procedures must be performed prior to randomization and the first dose of study drug. Screening laboratories will be performed at the local laboratory and may have been collected as standard of care within 48 hours prior to randomization, with the exception of serum creatinine determination, which must be obtained at the local laboratory within 24 hours of the first dose of study drug.

The following procedures will be performed at Screening:

- Obtain informed consent;
- Review all inclusion and exclusion criteria;
- Obtain medical/surgical history, including urological history; record inactive conditions diagnosed within the previous 5 years, complete urological/renal history, and all active conditions;
- Record prior and concomitant medications;
- Obtain demographics, including sex, age, race, and ethnicity;
- Perform a complete physical examination, including height and weight;
- Obtain vital signs, including blood pressure, heart rate, and respiratory rate;
- Assess clinical signs and symptoms;
- Perform pregnancy test for women of childbearing potential only;
- Collect blood samples for serum chemistry, hematology, and blood cultures;
- Collect urine sample by clean-catch midstream or other appropriate method that minimizes risk of bacterial contamination for urinalysis and urine cultures;
- Perform 12-lead ECG and consult the study Medical Monitor and local cardiologist in cases of clinically significant abnormal findings (eg, a QTcF >480 msec); and
- Assess adverse events.

6.3 Treatment Period – Day 1 to Day 14

All patients will receive randomized IV treatment q6h for 7 days (28 doses) or up to 14 days in patients with concurrent bacteremia.

6.3.1 Day 1

The following procedures will be performed at Day 1:

- Obtain vital signs, including blood pressure, heart rate, and respiratory rate;
- Collect PK sample, pre-dose;
- Administer imipenem/cilastatin;
- Collect pre-dose blood samples for:
 - Serum chemistry; and
 - Hematology;
- Collect pre-dose urine sample by clean-catch midstream or other appropriate method that minimizes risk of bacterial contamination for:
 - Urinalysis for all patients; and
 - Urine cultures for any patient who has received a single dose of a short-acting antibiotic in the 24 hours prior to randomization, or for patients who failed preceding antimicrobial therapy;

Note: this sample should be taken as close to randomization as possible (within 2 hours prior to randomization, if possible).

- Randomize patient to study drug via IRT;
- Administer imipenem/cilastatin;
- Administer study drug; and
- Assess adverse events.

6.3.2 Day 2

The following procedures will be performed at Day 2:

- Record concomitant medications;
- Perform a limited physical examination;
- Obtain vital signs, including blood pressure, heart rate, and respiratory rate;
- Assess clinical signs and symptoms;
- Collect blood sample for blood cultures, if applicable;
- Administer imipenem/cilastatin;
- Administer study drug; and
- Assess adverse events.

6.3.3 Day 3

The following procedures will be performed at Day 3:

- Record concomitant medications;
- Perform a complete physical examination, including weight;
- Obtain vital signs, including blood pressure, heart rate, and respiratory rate;
- Assess clinical signs and symptoms;
- Collect blood sample for:
 - Serum chemistry;
 - Hematology; and
 - Blood cultures, if applicable;
- Collect urine sample by clean-catch midstream or other appropriate method that minimizes risk of bacterial contamination for urinalysis;
- If PK samples will not be collected on Day 4, collect post-dose PK samples at the end of the infusion when the infusion pump is turned off, 0.5 hours after the end of the infusion, 2 hours after the end of the infusion, and 3 hours after the end of infusion (prior to the start of the next infusion);

Note: when possible, PK samples should be collected on Day 4. If not possible on Day 4, post-dose PK samples may be collected on Day 3 or Day 5 instead of Day 4, at the discretion of the Investigator.

- If PK samples are collected, perform 12-lead ECG as close as possible to the end of the infusion of study drug administration associated with the PK samples;
- Administer imipenem/cilastatin;
- Administer study drug; and
- Assess adverse events.

6.3.4 Day 4

The following procedures will be performed at Day 4:

- Record concomitant medications;
- Perform a limited physical examination;
- Obtain vital signs, including blood pressure, heart rate, and respiratory rate;
- Assess clinical signs and symptoms;
- Collect blood sample for blood cultures, if applicable;
- If PK samples were not collected on Day 3, collect post-dose PK samples at the end of the infusion when the infusion pump is turned off, 0.5 hours after the end of the infusion, 2 hours

after the end of the infusion, and 3 hours after the end of infusion (prior to the start of the next infusion);

Note: when possible, PK samples should be collected on Day 4. If not possible on Day 4, post-dose PK samples may be collected on Day 3 or Day 5 instead of Day 4, at the discretion of the Investigator.

- If PK samples are collected, perform 12-lead ECG as close as possible to the end of the infusion of study drug administration associated with the PK samples;
- Administer imipenem/cilastatin;
- Administer study drug; and
- Assess adverse events.

6.3.5 Day 5

The following procedures will be performed at Day 5:

- Record concomitant medications;
- Perform a complete physical examination, including weight;
- Obtain vital signs, including blood pressure, heart rate, and respiratory rate;
- Assess clinical signs and symptoms;
- Assess clinical outcome;
- Collect blood sample for:
 - Serum chemistry;
 - Hematology; and
 - Blood cultures, if applicable;
- Collect urine sample by clean-catch midstream or other appropriate method that minimizes risk of bacterial contamination for urine cultures;
- If post-dose PK samples were not collected on either Day 3 or Day 4, collect post-dose PK samples at the end of the infusion when the infusion pump is turned off, 0.5 hours after the end of the infusion, 2 hours after the end of the infusion, and 3 hours after the end of infusion (prior to the start of the next infusion);

Note: when possible, PK samples should be collected on Day 4. If not possible on Day 4, post-dose PK samples may be collected on Day 3 or Day 5 instead of Day 4, at the discretion of the Investigator.

- If PK samples are collected, perform 12-lead ECG as close as possible to end of the infusion of study drug administration associated with the PK samples;
- Administer imipenem/cilastatin;
- Administer study drug; and
- Assess adverse events.

6.3.6 Day 6

The following procedures will be performed at Day 6:

- Record concomitant medications;
- Perform a limited physical examination;
- Obtain vital signs, including blood pressure, heart rate, and respiratory rate;
- Assess clinical signs and symptoms;
- Collect blood sample for blood cultures, if applicable;
- Administer imipenem/cilastatin;
- Administer study drug; and
- Assess adverse events.

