Although local susceptibility testing is not a requirement, when local susceptibility testing indicates non-susceptibility to imipenem (eg, intermediate susceptibility or resistance to imipenem) but the patient is stable or clinically improving, the patient should remain on study drug at the discretion of the Investigator. Prior to discontinuation from study drug, the Investigator should discuss such cases with the Medical Monitor.

Day 1 is defined as the first day of study drug administration. The subsequent study days are defined by the number of calendar days thereafter. The duration of antibiotic treatment with study drug therapy will be 7 days (28 doses), with a prolongation of therapy up to 14 days if clinically indicated in patients with concurrent bacteremia.

All patients should receive at least 8 doses of IV study drug before the Investigator considers the patient to be a clinical failure and discontinues the patient from study drug therapy. No oral switch option is allowed. Patients who withdraw from study drug dosing should perform all End of

Treatment (EOT) Visit procedures and should be followed through the Late Follow-up (LFU) Visit for safety assessments, even if they withdraw from dosing due to clinical failure.

Throughout the study, all patients will be monitored for signs and symptoms of cUTI or AP and the occurrence of adverse events. Laboratory data, including chemistry panels, complete blood counts, and samples for urine and blood cultures, as well as electrocardiograms (ECGs), will be collected from all patients at specified times throughout the study.

Sparse PK sampling (ie, a total of 5 samples per patient) will be performed to refine the population PK model. To maintain the blind, PK samples will be collected from both treatment groups. Samples obtained from the ETX2514SUL group will be analyzed using a validated assay by a central bioanalytical laboratory.

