8.8 Electrocardiograms

Twelve-lead ECGs will be performed at baseline at Screening and repeated as close as possible to the end of the infusion of study drug administration on the day on which the post-dose PK samples are drawn (Day 3, Day 4, or Day 5; day selected at the discretion of the Investigator). All 12-lead ECGs will be performed after the patient has been in a supine position for at least 10 minutes. The value at Screening will be used for assessing the QTcF exclusion criterion. All 12-lead ECGs will be performed and read locally. The following ECG parameters will be recorded:

- Heart rate,
- QRS interval,
- PR interval,
- RR interval,
- QT interval, and
- QTc interval.

All ECGs will be evaluated for the presence of abnormalities by a qualified local physician. The ECGs will be classified as one of the following:

- Normal,
- Having a not clinically significant abnormality, or
- Having a clinically significant abnormality.

An example of a clinically significant abnormality may be a corrected QTcF >480 msec.

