18. The 12-lead ECG will be performed at baseline at Screening and repeated as close as possible to the end of the infusion of study drug administration on the day on which post-dose PK samples are drawn (Day 3, Day 4, or Day 5). The day on which the post-dose PK samples are drawn is at the discretion of the Investigator. All 12-lead ECGs will be performed after the patient has been in a supine position for at least 10 minutes.
19. Consult the Medical Monitor and local cardiologist in cases of clinically significant abnormal findings (eg, a QTcF >480 msec).
20. If baseline blood cultures were positive, repeat blood cultures should be obtained daily until negative or if the patient is a treatment failure.
21. An adequate clean-catch urine specimen for culture (or other appropriate method to collect a urine culture that minimizes risk of bacterial contamination) should be obtained at the specified time points. At any point in the study, if a patient fails while on therapy, a urine specimen should be obtained.
22. A repeat urine sample for culture must be obtained prior to the start of study drug treatment for any patient enrolled in the study who has received a single dose of a short-acting antibiotic in the 24 hours prior to randomization or for patients who failed preceding antimicrobial therapy. This sample should be taken as close to randomization as possible (within 2 hours prior to randomization, if possible).
23. Study drug should be administered q6h for a minimum of 7 days (28 doses), as described in the protocol.
24. All patients will be administered impipenem/cilastatin q6h.
25. Adverse events should be captured as described in the protocol.
26. PK samples will be collected immediately prior to the first dose of study drug on Day 1 and post-dose of any study drug infusion on Day 4 ( $\pm 1$  day) at the end of the infusion when the infusion pump is turned off, 0.5 hours after the end of the infusion, 2 hours after the end of the infusion, and 3 hours after the end of the infusion (prior to the start of the next infusion).

ECG = electrocardiogram; EOT = End of Treatment; IV = intravenous; LFU = Late Follow-up; PK = pharmacokinetics; q6h = every 6 hours; QTcF = QT interval corrected using Fridericia's formula; TOC = Test-of-Cure.

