### **8.12.4. Electrocardiograms**

Descriptive statistics will be provided for 12-lead ECG findings (heart rate, QRS, PR, RR, QT, and QTcF) and changes from baseline for each scheduled visit in the Safety Population.

Change from baseline will be calculated for each patient as the post-baseline value minus the baseline value. Boxplots by treatment group of the ECG parameters will also be provided for the baseline and post-baseline ECG assessments.

The number and percentage of patients with notable ECG changes in maximum QTcF ( $> 450$  msec,  $> 480$  msec, and  $> 500$  msec) over all post-baseline evaluations, as well as in QTcF maximum changes from baseline ( $> 30$  msec and  $> 60$  msec) over all post-baseline evaluations will be summarized by treatment group.

All 12-lead ECG findings will be listed by patient.

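### The one scheduled post-baseline ECG is tied to the PK draw, so patients who miss that draw or stop study drug before it have no scheduled on-treatment QTcF

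*Protocol*

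**What the plan says.** - **Visit lists.** Protocol 6.2 lists an ECG at Screening. The next ECG entries are in 6.3.3, 6.3.4 and 6.3.5 (Days 3, 4 and 5), each in practically the same words: "If PK samples are collected, perform 12-lead ECG as close as possible to the end of the infusion".
- **ECG section.** Protocol 8.8, and SAP 5.2.4 after it, place the single repeat ECG "on the day on which the post-dose PK samples are drawn (Day 3, Day 4, or Day 5"). Note 18 to SAP Table 1 likewise has it "on the day on which post-dose PK samples are drawn (Day 3, Day 4, or Day 5"). These passages contain no *if*; they use the PK day as the time point.
- **No other ECG.** None is listed for Day 1, Day 2, Day 6, Days 7-14/EOT, Test-of-Cure or Late Follow-up (Protocol 6.3.1 to 6.5). Patients who leave before completing study drug get the EOT assessments (Protocol 4.3 and 6.6). The EOT list in 6.3.7 has chemistry, hematology, urinalysis, vital signs, physical examination and adverse events, but no ECG.
- **General statements.** Protocol 3.1 says laboratory data, "as well as electrocardiograms (ECGs), will be collected from all patients at specified times throughout the study". It also says "Sparse PK sampling (ie, a total of 5 samples per patient) will be performed to refine the population PK model", with samples taken in both arms to keep the blind.
- **Analysis.** SAP 8.12.4 counts, by arm, maximum QTcF above 450, 480 and 500 msec and maximum increases above 30 and 60 msec, "over all post-baseline evaluations". It names no denominator. SAP 8.2 does not impute missing safety values.

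**The concern.** Safety is the primary objective, and Protocol 9.2.4 names change in ECG as a safety endpoint with an outlier analysis. A safety measurement should not depend on whether a sample for another purpose was obtained. As written, a failed or refused PK draw can take the ECG with it. A patient who stops study drug before the PK day has no later scheduled ECG, although the same patient still contributes laboratory tests, vital signs and an examination at EOT. ECG is the only one of these safety assessments without an EOT fallback.

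Two things are at stake. One is completeness, against the statement in Protocol 3.1 that ECGs come from all patients. The other is interpretation. Early stopping for an adverse event or failure is one route to a missing ECG, so the patients without one may not be a random subset. If percentages are taken over all treated patients, those with no ECG are also counted, without comment, as non-outliers.

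**Working it through.** The documents state no power or precision figure for QTcF, so there is nothing to reproduce. The check has three parts.

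**1. Who falls in the gap.** PK draws are planned for everyone, and Protocol 6.3.3 to 6.3.5 form a sequence: Day 4 preferred, Day 3 if Day 4 is known not to be possible, Day 5 if neither day was used. A patient still on drug through Day 5 misses the ECG only if no draw is made on any of the three days. A patient who stops before the planned PK day misses both, unless someone foresaw the stop and moved the draw to Day 3.

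**2. When early stops can happen.** For clinical failure, Protocol 3.1 says "All patients should receive at least 8 doses of IV study drug before the Investigator considers the patient to be a clinical failure". Dosing is every 6 hours with a 3-hour infusion:

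- Dose 8 starts at (8 − 1) × 6 = 42 h and ends at 42 + 3 = 45 h after the first dose starts.
- If the first dose starts at clock hour h on Day 1, dose 8 ends at h + 45. That is Day 2 if h < 3 (3 + 45 = 48) and Day 3 otherwise. It is never Day 4, because h < 24 gives less than 69 h and Day 4 begins at 72 h.

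Most patients who reach the 8-dose minimum therefore reach Day 3, inside the allowed window but before the preferred day. Stops for adverse events under Protocol 4.3 carry no dose minimum and can come earlier.

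**3. Effect on precision.** Inputs: about 80 patients randomized 2:1 (Protocol 9.2.6), so about 53 active and 27 placebo. The share without the ECG is not in the documents; 0% to 30% is an assumed range. With zero outliers among n patients, the one-sided 95% upper bound is 1 − 0.05^(1/n).

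| Assumed share missing | Active n | Upper bound | Placebo n | Upper bound |
|---|---|---|---|---|
| 0% | 53 | 5.5% | 27 | 10.5% |
| 5% | 50 | 5.8% | 26 | 10.9% |
| 10% | 48 | 6.05% | 24 | 11.7% |
| 20% | 42 | 6.9% | 22 | 12.7% |
| 30% | 37 | 7.8% | 19 | 14.6% |

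At 5-10% missing, 53 − 50 = 3 to 53 − 48 = 5 active patients have no ECG, and the bound rises by 0.3 to 0.55 percentage points.

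**Denominator.** Suppose 3 active patients are outliers and 10% have no ECG. The rate is 3/53 = 5.7% over all treated and 3/48 = 6.25% over those measured. SAP 8.12.4 does not say which applies, whereas SAP 8.12.2 does define the denominator for its liver-test counts.

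**The case against.** The strongest reply is that the *if* only selects the day. The sentence appears under Days 3, 4 and 5 because just one of them will be the PK day, every patient is meant to have a draw, and Protocol 8.8 and SAP note 18 set no condition. That stands, and it limits the gap to missed draws and early stops. It does not close it, because no text says what happens to the ECG when the draw fails.

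A second reply is that any single Day 3-5 assessment misses patients who stop before it. That also stands for the early-stop part: the cause there is the timing and the absence of an EOT fallback, not the PK link.

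Third, unscheduled ECGs are not prohibited, SAP 8.12.4 would count them, clinically significant ECG findings are reported as adverse events (Protocol 8.1), and the number of observations is shown for continuous summaries (SAP 8.1). So these patients have no *scheduled* QTcF, which is not the same as having none. None of these provisions guarantees a value.

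A reader might go further and infer that the ECG is optional for the whole trial, that patients failing after eight doses generally miss it, or that the QTcF counts will be biased. The documents do not support these readings. PK is planned for all, dose 8 usually ends on Day 3 inside the window, and nothing in the text gives a rate of missed draws or early stops or links early failure to QTcF.

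Protocol 7.9 and Appendix A are listed in the contents but could not be read here. A rule there on missed draws would narrow the point.

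**Conclusion.** The point holds as a limited gap in the collection of a safety endpoint. Patients whose PK draw is missed on Days 3-5, and patients who stop study drug before their PK day (mainly before or on Day 3), have no scheduled post-baseline QTcF. This does not fit the statement in Protocol 3.1 that ECGs are collected from all patients.

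The effect on precision is small: in the active arm, from 5.5% to about 6.05% at the upper end of an assumed 5-10% missing share. Selective loss of early stoppers is a reasonable worry in a trial whose primary objective is safety, but it remains a possibility without a figure. The case for change is that the remedy is cheap and makes the safety data more complete. It is not that the planned QTcF results would be invalid.

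**What to change.** 1. **Separate the ECG from the draw.** In Protocol 6.3.3 to 6.3.5 and 8.8, SAP 5.2.4, and SAP Table 1 (ECG row and note 18), require one end-of-infusion ECG on Day 4 (±1 day) in every patient on study drug, whether or not PK samples are drawn. Use the PK infusion when there is one.
2. **Add a fallback.** In Protocol 6.3.7 and 6.6 and SAP Table 1, add an ECG at the EOT or withdrawal visit only for patients who stop before that ECG is done, flagged as off-infusion.
3. **State the denominator.** In SAP 8.12.4, base QTcF percentages on patients with a post-baseline ECG, and for change also a baseline ECG. Report by arm how many have none and why. Summarise the off-infusion EOT values separately from the end-of-infusion values.

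Protocol Appendix A should be brought into line if it carries the same schedule.

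**Cost.** Wording changes to the protocol and SAP, with no ECG beyond the one post-baseline recording already planned per patient. The drawback is that an EOT ECG in an early stopper is not at peak exposure. It shows whether QTcF was abnormal at that visit but does not replace the end-of-infusion measurement.
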